8.1 Primary Endpoints

8.1.1 Primary Safety Endpoint

The primary safety endpoint is the occurrence rate of CEC-adjudicated, major radial access site complications attributed to study device or procedure through time of hospital discharge.

8.1.2 Primary Efficacy Endpoint

Technical success at the conclusion of the index procedure, defined as successful insertion of the S.M.A.R.T. RADIANT™ Vascular Stent System into the peripheral vasculature through the radial artery, successful deployment of the study device (S.M.A.R.T.™ stent) at the intended location, and successful withdrawal of the delivery system without conversion from radial to femoral artery access.

RADIANT / P21-7701

Version: 7.0 / March 21, 2023

8.2 Secondary Endpoints

8.2.1 Secondary Safety Endpoints

Secondary safety endpoints include the following:

- Peri-procedural (within 30 days post-index procedure):
 - Rate of device deficiencies for each of the three (3) devices
 - Rate of adverse events
 - Rates of death, index limb amputation and target lesion revascularization
 - Rate of procedural complications

Secondary Efficacy Endpoints

- Technical success associated with use of the BRITE TIP RADIANT™ Guiding Sheath, defined as successful insertion of the device into the peripheral vasculature through the radial artery (allowing for introduction of interventional and/or diagnostic devices) and successful withdrawal of the device.
- Procedural success associated with use of the SABERX RADIANT™ PTA Balloon Catheter for pre-dilation and/or post-deployment stent dilatation (whenever applicable), defined as successful insertion of the device into the peripheral vasculature through the radial artery, successful inflation and deflation of the balloon, successful withdrawal of the device, and achievement of a final residual diameter stenosis of < 30% at the conclusion of the index procedure.

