7.1 Inclusion Criteria

Subjects must meet ALL of the following inclusion criteria to be enrolled in the study:

1. Age \geq 18 years
2. For women of child-bearing potential, a negative pregnancy test within seven (7) days prior to the index procedure
3. Symptomatic leg ischemia or ischemic ulcerations that do NOT exceed digits of the foot (Rutherford/Becker Classification category 2, 3, 4 or 5)
4. Palpable radial artery with diameter \geq 2.5 mm, as assessed by duplex ultrasound
5. Eligibility for standard surgical repair, if necessary
6. A patient who requires a coronary intervention should have it performed at least seven (7) days prior to treatment of the target lesion
7. The patient must provide documented informed consent and any other documented authorization, as required, prior to initiation of the study procedure
8. Per Investigator assessment, the patient is willing and able to be followed up to 30 days post-procedure for evaluation and complete all required assessments per the study protocol.

Inclusion criteria 9 and 10 AND 11a through 14a OR 11b through 16b (whichever is applicable) would be assessed via baseline angiography performed at the time of index procedure:

9. The Investigator has assessed that the patient is a suitable candidate (i.e. meets all inclusion criteria and none of the exclusion criteria), for treatment of a lesion in the iliac, superficial femoral and/or proximal popliteal arteries via transradial approach and is eligible for conversion from a transradial to transfemoral approach, if it becomes necessary.
10. The guidewire is across the target lesion(s) and located intraluminally within the distal vessel following a transradial approach

Patients whose target lesion is in the iliac artery must meet these additional criteria prior to enrollment:

- 11a. A single *de novo* or restenotic lesion \geq 50% stenosis in the common and/or external iliac artery
- 12a. Stenotic lesion (one long or multiple serial/tandem lesions) \leq 100 mm, by visual assessment, within or across the common or external iliac arteries. The stenosis must be treatable with no more than two stents (while minimizing stent overlap)
- 13a. Reference vessel diameter (RVD) ranging from 4.0 to 9.0 mm by visual assessment

RADIANT / P21-7701

Version: 7.0 / March 21, 2023

Cordis®

14a. Angiographic evidence of a patent profunda or superficial femoral artery in the diseased (target) limb

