Exclusion criteria 20 through 25 would be assessed via baseline angiography performed at the time of index procedure:

20. Significant vessel tortuosity or other parameters prohibiting access to the lesion or 90° tortuosity which would prevent delivery of the stent device.
21. Noted perforation of the target vessel.
22. Stent placement required across or within 0.5 cm of the SFA/profundus femoris artery (PFA) bifurcation.
23. Cases of chronic total occlusion/in-stent restenosis/severe calcification in which there is pre-determined inability to treat the target lesion with a single stent, or procedures pre-determined to require stent-in-stent placement to obtain patency.
24. Presence of thrombus prior to crossing the lesion.
25. Successful PTA treatment of a target lesion in the SFA/PPA (defined as ≤ 50% stenosis after PTA treatment).

This study is designed to exclude children, pregnant women, and immunocompromised subjects, due to the nature of the procedure, device and indications.

8 Study Endpoints

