10.2.2 Screen Failures & Pre-Screen Failures

Pre-screen Failures: Pre-screen failures are defined as patients who are confirmed to not qualify for study participation according to the eligibility criteria after review of their medical records (i.e., prior to providing informed consent). Such subjects will neither be treated with the study devices nor followed per protocol.

RADIANT / P21-7701

Version: 7.0 / March 21, 2023

Screen Failures: Any consented patient who is confirmed to not qualify for study participation according to the eligibility criteria will be considered a screen failure and will neither be treated with the study devices nor followed per protocol.

Signed informed consent forms and all applicable documentation including source records indicating rationale for screen failure classification and Screening/Enrollment logs or equivalent forms/screens in the Electronic Data Capture (EDC) system will be reviewed during monitoring visits for all screen failure patients.

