6.0 – 7.0 mm	8 mm
7.0 – 8.0 mm	9 mm
8.0 – 9.0 mm	10 mm

Note: Refer to product labeling for stent length information

- 3. Insertion of BRITE TIP RADIANT Guiding Sheath or Guide Catheter and Guidewire**
 - a. Access the treatment site utilizing the appropriate accessory equipment compatible with the 6F (2.0 mm) delivery system.
 - b. Place a 6F guiding sheath of an appropriate length (110cm for a 150cm long delivery system and a 135cm for a 190cm long delivery system) with an internal diameter of at least 2.2 mm.
 - c. Place an .018" (0.46 mm) guidewire of sufficient length across the lesion to be stented via the guiding sheath or guide catheter.
- 4. Dilation of Lesion with SABERX RADIANT PTA Balloon Catheter (if appropriate)**
 - a. Pre-dilate the lesion using standard PTA balloon catheter techniques.
 - b. Remove the PTA balloon catheter from the patient while maintaining lesion access with the guidewire.
- 5. Stent Deployment**
 - a. Verify that the delivery system's radiopaque stent markers (leading and trailing ends) are proximal and distal to the target lesion.

RADIANT / P21-7701

Version: 7.0 / March 21, 2023

- b. Initiate stent deployment by rotating the thumbwheel in a clockwise direction while holding the handle in a fixed position.
- c. While using fluoroscopy, maintain position of the radiopaque stent markers relative to the target lesion site. Watch for the distal radiopaque markers to begin separating. Separation of the distal stent markers signals that the stent is deploying. Continue turning the tuning dial to cause further separation of the distal radiopaque markers until the distal end of the stent obtains full wall apposition.
- d. Deployment is complete when the proximal markers oppose the vessel wall and the outer sheath radiopaque marker is proximal to the support member stent stop.

6. Post-deployment Stent Dilatation with SABERX RADIANT PTA Balloon Catheter (if appropriate)

- a. While using fluoroscopy, withdraw the entire delivery system as one unit, over the guidewire, into the guiding sheath and out of the body. Remove the delivery device from the guidewire. Do not rotate the handle during withdrawal.
- b. Using fluoroscopy, visualize the stent to verify full deployment. Post-deployment balloon dilatation can be performed within the stent at any point along the lesion where there was incomplete expansion.

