13.6 Device Deficiencies

A device deficiency is any inadequacy in the identity, quality, durability, reliability, safety or performance of an investigational device, including device malfunction, use errors or inadequacy in information supplied by the manufacturer.

- A device malfunction is considered a failure of a device to meet any of its performance specifications or otherwise perform as intended. Performance specifications include all claims made in the Instructions for Use (IFU)/Investigator's Brochure (IB)/clinical study protocol.

In the event of a device deficiency, detailed information on the product, circumstances of the deficiency as well as any complications and their management will be collected and reported.

Though subjects are considered enrolled only from the time they are confirmed to qualify for study participation according to the eligibility criteria (i.e., upon completion of angiography), all device deficiencies for all enrolled subjects, including those from the "roll-in" cohort of the study, will be reported retroactive to the initial use or handling of a study device until their exit from the study (i.e., point of study completion or premature discontinuation).

The Investigator must report all new device deficiencies or changes to previously-reported device deficiencies (based on any new findings), with whatever information is available at the time, to the sponsor and/or designee by any acceptable method as communicated by them, within 24 hours or one working day of first awareness of the event by the study team at the institution and provide any additional information as required by the sponsor/designee. If the event is not reported through the EDC system within this time

RADIANTY / P21-7701

Version: 7.0 / March 21, 2023

period, it must be done so as soon as possible. If applicable, the Investigator must make arrangements for the safe return of any malfunctioned, damaged, and/or unused investigational devices in accordance with the instructions provided by the sponsor.

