**6 ANALYSIS POPULATION**

Analyses for the endpoints will be performed using the intent-to-treat (ITT) population. The ITT population will consist of all subjects enrolled in the study, excluding roll-ins, and for whom a device insertion was attempted, regardless of the treatment actually received.

The per-protocol analysis population is defined as a sub-group of the ITT population consisting of subjects without protocol deviations that could possibly affect the primary endpoints. Primary endpoint analysis using this population is supportive in nature.

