### **8.5.2 Secondary Effectiveness Endpoint Analysis**

The secondary endpoint of technical success of the BRITE TIP RADIANT™ Guiding Sheath will be summarized on a per subject basis since the guiding sheath would not be completely removed between lesion treatments of a bilateral subject. The number of successfully inserted BRITE TIP RADIANT guiding sheaths will be counted and divided by the number of BRITE TIP RADIANT guiding sheaths with attempted insertions to estimate the technical success. A two-sided 95% exact confidence interval will be constructed about the technical success rate. The confidence interval will be calculated using the Clopper-Pearson method.

Procedural success of the SABERX RADIANT™ PTA Balloon Catheter will be summarized on a per limb basis. In the case where pre-dilation and post-dilatation are performed and/or more than one SABERX RADIANT balloon was used to treat a lesion, each device must be successfully inserted into the peripheral vasculature through the radial artery, successfully inflated and deflated, and successful withdrawn with the achievement of a final residual diameter stenosis of < 30% for the treated lesion. The number of successful procedures using the SABERX RADIANT™ PTA Balloon Catheter will be calculated for each limb. A two-sided 95% exact confidence interval will be constructed about the procedural success rate. The confidence interval will be calculated using the Clopper-Pearson method.

No formal hypothesis testing will be done on the secondary effectiveness endpoints.

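### Sheath success and device-deficiency rates are computed in enrolled subjects only, so a sheath failure that prevents enrolment is never counted and the insertion rate is biased upward by an undocumented amount

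*Protocol*

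**What the plan says.** **Population.** SAP 6 runs the endpoint analyses in ITT: "The ITT population will consist of all subjects enrolled in the study, excluding roll-ins, and for whom a device insertion was attempted". Protocol 14.1 says the same without mentioning roll-ins.

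**Enrolment.** Protocol 10.3 requires radial puncture and assessment against all eligibility criteria, including the angiographic ones. Inclusion criterion 10 (7.1) reads: "The guidewire is across the target lesion(s) and located intraluminally within the distal vessel following a transradial approach". A consented patient who does not qualify "will be considered a screen failure and will neither be treated with the study devices nor followed per protocol" (10.2.2). Under 11.4 the site tells the sponsor after the procedure whether the patient was enrolled or was a screen failure.

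**Procedure.** Step 3 of protocol 11.1 places the guiding sheath and then a "guidewire of sufficient length across the lesion to be stented via the guiding sheath or guide catheter". The closing note of 11.1 makes BRITE TIP the required guiding sheath, and SABERX the required balloon if any dilation is done.

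**Sheath endpoint.** Protocol 8.2 has two components, insertion and withdrawal. The insertion component reads: "successful insertion of the device into the peripheral vasculature through the radial artery (allowing for introduction of interventional and/or diagnostic devices". SAP 8.5.2 takes the number of sheaths successfully inserted, "divided by the number of BRITE TIP RADIANT guiding sheaths with attempted insertions to estimate the technical success". Withdrawal does not enter that calculation.

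**Deficiencies.** Protocol 13.6 back-dates reporting to the first use or handling of a study device, but for "all device deficiencies for all enrolled subjects".

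**Balloon.** The SABERX endpoint is insertion, inflation and deflation, withdrawal, and final residual stenosis below 30% at the end of the procedure. Exclusion criterion 25 (7.2) removes "Successful PTA treatment of a target lesion in the SFA/PPA", defined as at most 50% stenosis after PTA in section 7.2 but as below 50% in the synopsis.

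**The concern.** A device success rate should count every attempt to use the device. Here the analysed set is formed after the sheath may already have been used, and one condition for entering it, a wire across the lesion by the radial route, can depend on the sheath having worked. An attempt that fails and prevents crossing therefore drops out of the success rate and, through 13.6, out of the deficiency rate as well. The bias has one direction: the sheath looks better than it is.

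For the balloon the issue is narrower. If an SFA/PPA lesion is pre-dilated before enrolment is settled, criterion 25 removes the lesions that PTA opened, and the remaining pre-dilated limbs are a selected group that responded poorly.

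At stake is what the trial can say about the sheath and balloon by the radial route. Protocol 8.4 ties these endpoints to the primary objective, and 14.3 sets a goal of 30 uses to characterise SABERX. No hypothesis test depends on them.

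**Working it through.** **1. The plan's own figure.** No sample size, power or expected rate is stated for the sheath or balloon endpoints. The 129 comes from the primary endpoints. With 98% against 93%, one-sided 0.05, exact binomial, n = 129 needs at least 125 successes; the exact alpha is 0.0481 and the power 88.2%, matching the stated 88%. It serves below only as the size of the analysed set, taking one sheath per subject.

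**2. Path of a failed sheath.** Insertion attempted (11.1, step 3) → sheath fails and the wire cannot be passed → criterion 10 not met (7.1) → not enrolled (10.3) → screen failure (10.2.2) → outside ITT (SAP 6), and so outside SAP 8.5.2 and the deficiency rates of SAP 8.4.2. A case rescued by a second sheath or a guide catheter can meet criterion 10 and stays in.

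**3. Size of the effect, by assumption.** Let s be the true insertion success and L the share of insertion failures still enrolled. The documents give neither.

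- Observed rate = s / (s + (1 − s)L)
- Attempts behind 129 enrolled = 129 / (s + (1 − s)L)
- Patients unseen = attempts − 129

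| True s | L = 0: observed (unseen) | L = 0.5: observed (unseen) | L = 1: observed |
|---|---|---|---|
| 90% | 100% (14.3) | 94.7% (6.8) | 90% |
| 95% | 100% (6.8) | 97.4% (3.3) | 95% |
| 98% | 100% (2.6) | 99.0% (1.3) | 98% |

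Worked line: s = 0.95 and L = 0.5 give 0.95 / (0.95 + 0.05 × 0.5) = 0.95 / 0.975 = 97.4%; attempts 129 / 0.975 = 132.3; unseen 3.3.

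For 129/129 the exact two-sided 95% lower bound is 0.025^(1/129) = 97.2%. With L = 0 the interval 97.2% to 100% therefore excludes a true 95% or 90% and covers a true 98%.

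**4. Balloon.** In SFA/PPA limbs dilated before enrolment and retained, none has a PTA result that criterion 25 counts as successful; that follows from the rule. The endpoint is different. Write m for mechanical success and g for a final residual below 30% after stenting, and multiply them as if independent. With m assumed at 0.95 to 1.00 and g at 0.90 to 0.98, success in retained limbs runs from 0.95 × 0.90 = 86% to 1.00 × 0.98 = 98%. Criterion 25 does not apply to iliac limbs, and post-deployment dilation comes after the step it concerns.

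**5. Order of enrolment and device use.** The passages do not agree:

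- 7.2 says criteria 20 to 25 are read on baseline angiography, yet criterion 25 is a result after PTA.
- 10.2.2 says screen failures are not treated with study devices, which cannot hold for a patient excluded after SABERX dilation.
- 11.1 and 13.6 place enrolment at completion of angiography but back-date deficiencies to earlier device handling.
- 11.4 settles enrolment status after the procedure.

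**The case against.** **Sequence.** The steps of 11.1 cannot be strict chronology, since step 1 is balloon angioplasty and the sheath appears only in step 3. Step 3 also allows a guide catheter, so criterion 10 does not prove that BRITE TIP worked, and 10.2.2 can be read as placing enrolment before any device use. This stands as far as it goes: the order is unsettled. But 13.6 expressly provides for device handling before enrolment, so the loss is possible under the plan as written.

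**Tempting stronger readings.** A reader might infer that sheath success is close to 100% by construction. The documents do not support that. Rescued cases stay in, a failed first sheath in an enrolled subject counts among attempted insertions, and withdrawal in protocol 8.2 is not conditioned on. That last limit is weaker in practice, because SAP 8.5.2 leaves withdrawal out.

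A reader might also infer that femoropopliteal pre-dilation keeps only balloon failures. It keeps lesions that PTA did not open. The endpoint asks for mechanical function and a final residual below 30%, which such limbs can meet. Section 11.1 also ties stenting to a technically successful angioplasty, which favours retaining mechanical successes. If enrolment closes before pre-dilation, even this selection disappears.

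Nor is the complement of the 93.2% in protocol 5.4.1 a sheath-failure rate. That figure is overall success across a range of peripheral interventions, and 5.4.2 attributes access failure typically to puncture error or spasm.

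**Already handled, and low stakes.** Protocol 17.1 requires opened product and device deficiencies to be recorded in the CRFs, so some of the data may exist. No analysis set takes them in. Protocol 14.4.2 and 14.5 make these endpoints untested, hypothesis-generating and not for labelling, which limits the importance of the point without removing the bias.

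**Conclusion.** The point holds for the sheath and for the deficiency rates. An attempt that fails and prevents crossing is absent from both, and the SAP calculates only the insertion component, so the reported rate can err only upward from this cause. The size is undocumented. Under the assumed inputs it runs from none (all failures still enrolled) to a rate of 100% whatever the truth (none enrolled); a true 95% shows as 97.4% if half are enrolled.

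For SABERX the conclusion is conditional. If SFA/PPA pre-dilation precedes enrolment, the limbs it contributes are a selected set of poorly responding lesions. Iliac limbs and post-dilation are unaffected. The primary endpoints are not part of this point. It is an inexpensive improvement to two descriptive endpoints and the deficiency rates.

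**What to change.** - In SAP 6, 8.4.2 and 8.5.2, define the BRITE TIP denominator as all consented non-roll-in patients with an attempted sheath insertion, and the SABERX denominator as all limbs with an attempted SABERX use, whether or not later enrolled. The word is attempted, because a set of inserted devices would again condition on success. Roll-in status is fixed before enrolment, so screen failures can be classified.
- In these sets report sheath insertion and sheath withdrawal, SABERX mechanical success (insertion, inflation, deflation, withdrawal) and the deficiency rates. State how a patient with more than one attempted sheath is counted, since SAP 8.5.2 speaks of both subjects and sheaths.
- Report the final residual below 30% separately, in limbs that completed the study procedure.
- Amend protocol 10.2.2 and 13.6 so that the device and deficiency CRF pages are completed for screen failures exposed to a study device.
- Reconcile protocol 7.2, 10.2.2, 10.3, 11.1 and 11.4 on when enrolment occurs relative to device use, and the two cut-offs of criterion 25 (synopsis and 7.2).
- Keep ITT for both primary endpoints.

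Cost: SAP wording, a protocol clarification and a few CRF pages for a small number of patients. The sheath rate may come out slightly less favourable.

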8.3 Additional Data Points

Data will be collected to evaluate the following health economics outcomes:

- Fluoroscopy time and procedural time, defined as the time of sheath introduction to time of vascular closure.
- Time to achieve hemostasis,
- defined as the time elapsed from removal of the BRITE TIP RADIANT™ Guiding Sheath to the time that hemostasis was first observed. Time to ambulation, defined as when the subject can stand up and walk any distance
- Time to hospital discharge
 - Time to hospital discharge eligibility (when physician examines and if all is well, gives discharge orders).

Method to achieve closure of the transradial artery access site

Quality of Life Assessments: Data will be also collected to evaluate health-related, quality-of-life in all subjects by administering the 36-item Short Form Health Survey (SF-36) and the EuroQOL-5 Dimension (EQ-5D) standardized, validated questionnaires to assess general and disease-specific outcomes. Brief descriptions of these two questionnaires are as follows

- The SF-36 is a patient-reported survey of general health and well-being. It consists of 36 items grouped in these dimensions: physical functioning, physical and emotional limitations, social functioning, bodily pain, general and mental health. Higher scores indicate better health status.
- The EQ-5D questionnaire is used for the assessment of health state utility and visual analog rating, which is a quantitative measure of overall health status. It consists of five (5) dimensions: mobility, self-care, usual activities, pain/discomfort and anxiety/depression.

